- a. Participants will be advised to reach out to the study team if they forget their login.
3. a brief orientation to the app with suggested guidance for usage

Participant App Usage: Participants will be asked to use the Messy Memories app for 6 weeks beginning the day that all components of the Baseline Visit are complete. This date marks the start of the intervention. Participants will be advised of the date which marks the end of the intervention (6 weeks later). They will be asked to focus on their memory of their ICU experience for memory processing. They will be asked to use the app at least 3 days a week for at least 30 minutes each day. They will be instructed to stop using and delete the app from their phones when their study participation ends.

Post-Baseline Check-In: Participants will receive a phone call from study staff within one week of the baseline assessment to confirm that they are not experiencing any technical difficulties with the app. If a participant expresses distress related (or not related) to the app, study staff will follow safety protocol by sharing the IRB-approved list of resources with the participant over the phone and/or via email and will consult with the study PI.

“Visit 2”/3-Week/Mid-Intervention Questionnaire (Approximately 25 minutes): Approximately three weeks after the start of the intervention (Baseline Visit) participants will be asked to complete a questionnaire by telephone or video consisting of the PCL-5, PHQ-8, GAD-7, ASI, IPAQ, and PSQI. If a participant expresses that they will not be available to complete the questionnaire by telephone or video, or if the study team is unable to reach the participant, the study team will send the questionnaire to the participant via Qualtrics. Those who do not complete the survey will remain on the study, and this task will be listed as “not completed” and included as part of analysis.

6-Week/End of Intervention Call: A member of the study team will call the participant within one week prior to the end of the intervention to remind the participant of the date when the intervention ends and that they are to stop using the Messy Memories app at that time. This call can also be used to schedule the 6-week/Post-Intervention Questionnaire.

“Visit 3”/6-Week/Post-Intervention Questionnaire (Approximately 40 minutes): Approximately six weeks after the start of the intervention (Baseline Visit) participants will be asked to complete another questionnaire by telephone or video consisting of the PCL-5, PHQ-8, GAD-7, ASI, IPAQ, PSQI, substance use measures, implementation measures (e.g., feasibility, acceptability, appropriateness, satisfaction), and qualitative feedback on the intervention (e.g., likes, dislikes, suggestions for improvement). If a participant expresses that they will not be available to complete the questionnaire by telephone or video, or if the study team is unable to reach the participant, the study team will send the questionnaire to the participant via Qualtrics. Those who do not complete the survey will remain on the study, and this task will be listed as “not completed” and included as part of analysis.

“Visit 4”/12-Week/Follow-Up Questionnaire (Approximately 30 minutes): Approximately six weeks after the end of the intervention, participants will be asked to complete one final questionnaire by phone consisting of the PCL-5, PHQ-8, GAD-7, ASI, IPAQ, PSQI, and substance use measures. If a participant expresses that they will not be available to complete the questionnaire by telephone or video, or if the study team is unable to reach the participant, the study team will send the questionnaire to the participant via Qualtrics. Those who do not complete the survey will remain on the study, and this task will be listed as “not completed” and included as part of analysis.

Compensation:

Participants will be compensated a total of \$120 if they complete all components of the study in the form of TruCentive electronic gift cards. This compensation will be allocated in the following amounts:

- \$30 for completion of all components of the Baseline Visit (completing questionnaires, downloading the app, and being onboarded to the app with study staff)
- \$30 for completion of the 3-Week/Mid-Intervention Questionnaire
- \$30 for completion of the 6-Week/Post-Intervention Questionnaire
- \$30 for completion of the 12-Week/Follow-up Questionnaire

Participants who complete only part of a questionnaire (50%, for example) will *not* receive partial compensation for that questionnaire. Participants may, however, skip any question(s) that they do not feel comfortable answering, and this will not impact their compensation for the study.

All compensation will be provided via TruCentive e-gift cards sent to subjects by email, SMS text message or both. Each TruCentive electronic gift card will allow participants to choose from a list of pre-approved businesses at which they may use each card (including Target, Amazon, Starbucks, Chipotle, etc.).

Participants will receive instructions for utilizing TruCentive.

5. Risks

Study procedures (i.e., completing questionnaires such as the PCL-5, answering Messy Memories app questions, and, as applicable, recording and processing distressing memories of prior ICU experiences in the *Messy Memories* app) present minimal risk. Exposure treatments pose some risk of psychological discomfort, but participants will not be required to interact with the app any more than they choose to and can discontinue using the app at any time without penalty. The questions asked and the thoughts evoked during the course of this research study pose minimal risk of psychological discomfort, and participants may skip any question or questionnaire that they choose. Participants will be made aware of these risks and will be assured that they can terminate their participation in the study at any time without penalty. Mental health resources will be provided to all participants.

A potential risk of this study is violation of participant privacy, since patient medical information will be used as a source of data. Special protections against this risk will be provided (see below). Although the *Messy Memories* application does not directly collect or store protected health information, it is possible that participants may enter personally identifiable information into the free text fields within the application. To mitigate against this, participants will be instructed not to enter any personally identifiable information into the free text fields at any time while using the application. In addition, direct recordings of participants' prior distressing memory (audio recorded) will **not** be stored on the *Messy Memories* application nor collected as study data. The study-provided login to access the *Messy Memories* app will **not** contain any identifiable information. Participants will contact the study team if they require any assistance with the study login.

6. Benefits

There is no direct benefit to subjects who participate in this study.

Improved psychological symptoms and adherence to health behaviors: Participants may benefit from the intervention in terms of decreased psychological distress and posttraumatic stress disorder (PTSD) symptoms related to their prior critical illness. This may help participants become more adherent to their medical treatments and develop adaptive health behaviors. Participants may also benefit from the attention they receive from study personnel.

Contributions to scientific/medical knowledge: While participants in this study may not directly benefit from their participation, we anticipate the results from this study will benefit future research seeking to reduce psychological distress and improve health behaviors after prior critical illness experiences.

7. Alternatives

The alternative is not to participate in the study. Participants will be assured that they can decide at any point to discontinue participation with absolutely no consequences. Additionally, the Principal Investigator may withdraw participants from the study after enrollment upon further examination of eligibility criteria and/or at their professional discretion.

8. Data and Safety Monitoring

As this study presents minimal risk to participants, data and safety monitoring will be conducted by the study staff as directed by the principal investigator. Investigators and research staff will meet weekly to discuss any issues or concerns with the study, in particular, whether there were any unexpected complaints about the study procedures or questionnaires, or whether there were any breaches in data confidentiality (which will be reported to the IRB as required by policy). If unexpected complaints about the procedures or questionnaires are generated, then the study may be stopped or altered prior to recruiting the full sample.

The Study Principal Investigator (PI), [name], and [name], a board-certified general internist, will be responsible for ensuring participants' safety. The investigators will be informed of unanticipated problems or unexpected serious adverse events that may be related to the study protocol as soon as they occur, and they will notify the Institutional Review Board, in compliance with policy.

If participants incidentally disclose that they are experiencing severe symptoms related to anxiety, depression, psychological distress, or suicidal ideation at any point in the study the study team will follow a standardized safety protocol. This will include reminding participants of available mental health resources provided at the beginning of the study to all participants, offering a phone call with a study PI/MD within 24 hours, encouraging participants to stop using the Messy Memories app if they feel it is causing excessive distress, and encouraging participants to seek medical and/or psychological care with a doctor or mental health professional. All instances of incidentally reported severe psychological distress will be communicated to a Study PI/MD within 24 hours. The Study PI/MD will determine next steps and follow-up with the participant as deemed appropriate.

The study team will collect required demographic data to report to the NIA as required via CROMS (Clinical Research Operations and Management System).

A description of the study will be available on <http://www.ClinicalTrials.gov>, as required by U.S. Law. This website will not include information that can identify participants. At most, the website will include a summary of the results.

References

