Health behaviors: The International Physical Activity Questionnaire (IPAQ),⁷² will be used to measure the type, frequency, and intensity of daily physical activity. The Pittsburgh Sleep Quality Index (PSQI)⁷³ will be used to measure total sleep duration and sleep quality. Participants will also be asked to report on their patterns of tobacco, alcohol, and substance/drug use.

Post-ICU support: As part of the baseline visit, participants will be asked questions about any medical, psychological, and social support that they may have received after their prior ICU admission. Participants will also be asked about what forms of post-ICU support they think would be helpful for patients and their families.

Sociodemographic and clinical characteristics: Participant sociodemographic information (e.g., age, sex, gender, sexual orientation, race, ethnicity, primary language, educational attainment, occupation, annual household income, marital/partner status, living situation, insurance status) will be self-reported at screening. Participants will also be asked to self-report any comorbid medical or psychiatric conditions, as well as provide information about their prior ICU admission (e.g., location, primary diagnosis, duration of hospitalization, need for intubation/mechanical ventilation, need for renal replacement therapy, need for central line placement).

3. Statistical Procedures

General approach: Given that this pilot study is, by design, not powered to test the effect of our intervention on study outcomes, we do not intend to publish analyses of these effects. Although some have used pilot studies to estimate effect sizes on primary outcomes, we agree with leaders in our field who argue that effect size estimates from small pilot studies are too imprecise to meaningfully inform effect size assumptions or power analyses for larger, later-stage studies. Therefore, we do not provide power calculations for the effects of our intervention on study outcomes. However, we will use estimates from these studies (e.g., standard deviations, attrition rates) to help determine appropriate sample sizes for a future study that is powered to detect meaningful reductions in measures of psychological distress following critical illness.

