Descriptive statistics: Categorical data will be presented as percentages and continuous data will be presented as means with standard deviations for normally distributed measures and as medians with interquartile ranges for measures that are not normally distributed. Checks of assumptions (e.g., normality) underlying statistical procedures will be performed and corrective procedures will be applied (e.g., log transformations, nonparametric tests).

Outcomes: The primary outcomes are feasibility and acceptability of the *Messy Memories* intervention and research procedures. Feasibility will be based on participant recruitment, retention, and completion rates of $\geq 70\%$. Acceptability will be based on participant satisfaction ratings of $\geq 70\%$ and qualitative analysis of exit survey responses. The *exploratory outcome* is the ability of the *Messy Memories* intervention to engage the proposed mechanistic target, which will be based on pre-/post-intervention change in patient-reported PTSD symptoms specifically triggered by the prior critical illness and ICU hospitalization.

Aim 1: Assess the feasibility of recruiting and engaging critical illness survivors in a mobile application-based exposure therapy intervention (*Messy Memories*). **Hypothesis:** The intervention will be feasible based on recruitment, retention, and completion rates of $\geq 70\%$.

Aim 2: Assess the acceptability of recruiting and engaging critical illness survivors in a mobile application-based exposure therapy intervention (*Messy Memories*). **Hypothesis:** The intervention will be acceptable based on participant satisfaction ratings of $\geq 70\%$ and qualitative analysis of exit survey responses.

Statistical approach for Aims 1 & 2: We will calculate means and standard deviations (or medians and interquartile ranges if variables are non-normal) as well as frequencies and proportions to assess feasibility and acceptability outcomes. T-tests or chi-square tests will be used to compare the demographic and clinical characteristics of 1) eligible patients who did vs. did not enroll in the study and 2) consenting participants who did vs. did not complete the study. Free-text responses from the exit survey will be described qualitatively and used to contextualize our quantitative results and guide future research.

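### The protocol requests two different daily minimums of app use (10 and 30 minutes); separately, retention, completion, attrition and satisfaction need definitions

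*Combined protocol and SAP*

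**What the plan says.** **App use.** Section 2 (Intervention) asks participants to use the app on three or more days a week, with a minimum of 10 minutes on each of those days, over a 6-week intervention. Section 4 (Participant App Usage) gives the same number of days and the same 6 weeks, but a minimum of 30 minutes a day. Section 2 (Measures, Feasibility) plans to describe how often and for how long participants engage with each feature. Section 1 lists the ability to follow the intervention protocol among the things the study will test.

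**Feasibility rates.** Section 3 (Outcomes) states: "Feasibility will be based on participant recruitment, retention, and completion rates of" at least 70%. The Measures list offers a natural definition of recruitment (eligible people who accept) but contains no follow-up retention or completion rate. Section 3 (Aims 1 & 2) will compare "consenting participants who did vs. did not complete the study", and the Compensation text in Section 4 pays the full amount to participants "if they complete all components of the study". For each of the Week 3, 6 and 12 questionnaires, Section 4 says: "Those who do not complete the survey will remain on the study". The same sentence goes on to record the task as not completed and to carry it into the analysis.

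**Attrition.** Section 3 (General approach) says "we will use estimates from these studies (e.g., standard deviations, attrition rates) to help determine appropriate sample sizes for a future study". Attrition is not defined.

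**Acceptability.** Section 3 (Outcomes) states: "Acceptability will be based on participant satisfaction ratings of" at least 70%, together with qualitative analysis of the exit survey. Section 2 (Measures) separately treats an average of 4 or more on the Acceptability of Intervention Measure (AIM) as indicating adequate acceptability. The Week 6 visit lists acceptability and satisfaction as separate items, and no satisfaction instrument is named.

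**The concern.** The amount of app use requested is the dose of the intervention being piloted. If the text gives two amounts, a statement that participants did or did not use the app as asked has no fixed meaning. Participants could also be instructed differently depending on which section a staff member or a mailed tip sheet follows. The pilot is meant to refine the protocol for a later trial, so the requested amount needs to be known.

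The secondary issue is that two of the three feasibility rates can be counted in more than one way. Keeping non-responders on the study is sensible conduct, but it leaves open whether a person who returns no questionnaire counts as retained. The compensation text is the nearest thing to a definition of completion, and it is payment text. Participants may "skip any question(s) that they do not feel comfortable answering, and this will not impact their compensation for the study", and Section 5 adds that "participants may skip any question or questionnaire that they choose". What counts as an obtained questionnaire therefore also has to be said. For acceptability, 70% could be a share of participants or a score.

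**Working it through.** **1. Requested app use.** Inputs: 3 days a week and 6 weeks (both sections); 10 minutes (Section 2, Intervention); 30 minutes (Section 4, Participant App Usage). Minimum total = days per week × minutes per day × weeks.

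| Source | Per week | Over 6 weeks |
|---|---|---|
| Section 2, Intervention | 3 × 10 = 30 min | 30 × 6 = 180 min |
| Section 4, Participant App Usage | 3 × 30 = 90 min | 90 × 6 = 540 min |

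The ratio is 540/180 = 3 and the gap is 540 − 180 = 360 minutes. A participant who uses the app for exactly 180 minutes on the stated schedule has met 100% of one request and 180/540 = 33.3% of the other.

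**2. Retention at the minimum sample size.** Section 3 sets a minimum of n=30 on pragmatic grounds with no formula, so there is no planned precision figure to reproduce. The pass line is 0.70 × 30 = 21. The documents give no response rates; those below are assumptions.

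- On-study count with *w* withdrawals: (30 − *w*)/30. This is 100% for *w* = 0, 70.0% for *w* = 9 (pass) and 66.7% for *w* = 10 (fail).
- Questionnaire count with nobody withdrawn: 21/30 = 70.0% passes (exact 95% CI 50.6% to 85.3%); 20/30 = 66.7% fails. The on-study count is 100% in both cases.
- Assumed steady loss of 24, 22 and 18 of 30 at Weeks 3, 6 and 12: Week 6 gives 22/30 = 73.3% (pass) and Week 12 gives 18/30 = 60.0% (fail). Completing every component cannot exceed the lowest visit, so it is at most 60.0% (fail).

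The choice of visit can therefore change the result, as can the choice between on-study status and questionnaires.

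**3. The 70% satisfaction figure.** Assume, for illustration only, a 1–5 rating like that of the AIM.

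- As a share of people rating 4 or more: 21 people at 4 and 9 at 3 give 21/30 = 70.0% with mean (84 + 27)/30 = 3.70. In the other direction, 20 at 5 and 10 at 2 give 20/30 = 66.7% with mean (100 + 20)/30 = 4.00.
- As a score: 70% of the maximum is 0.70 × 5 = 3.5, and 70% of the range is 1 + 0.70 × 4 = 3.8. Both lie below the AIM cut-off of 4.

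These cases apply two rules to one set of ratings, whereas satisfaction and the AIM are listed separately. They show only that the meaning of 70% matters.

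**The case against.** **On app use.** Both figures are minimums, and Section 5 lets participants use the app as little as they choose. Someone who meets the larger request meets both, and none of the six listed feasibility measures carries a minutes threshold. This stands as far as it goes: no 70% result is shown to change because of the contradiction. It does not remove the contradiction, because the two texts still instruct participants differently and duration of use is to be reported.

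**On retention.** A reader might infer that the plan lets retention pass automatically, or that it conceals attrition. The documents do not support either. No section says retention is counted by on-study status, and an on-study pass would still need at most 9 of 30 to withdraw. Missed tasks are flagged and analysed, and completers are compared with non-completers, so the loss can be recovered. The separate completion criterion may also catch it, as it would in the steady-loss example if completion means all components. What stands is the missing definition.

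**On the later trial.** A reader might infer that it would be undersized and lose power. That would require the team to ignore its own flags and plan on zero attrition, which no section proposes. The pilot's estimates are only to help with sizing.

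**On acceptability.** A reader might infer two rival criteria that must both be met. The Outcomes paragraph and the Aim 2 hypothesis tie acceptability to satisfaction plus qualitative analysis; the AIM cut-off appears only under Measures, as an indication. What stands is the unnamed item, the meaning of 70% and the unstated role of the AIM.

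**Conclusion.** The app-use text is wrong as written: two sections give daily minimums that differ threefold, or 360 minutes over the intervention. That total assumes exactly the minimum three days in each of 6 weeks; the threefold ratio holds for any common number of days. The consequence is that reported engagement has no single reference amount. This review takes no position on which figure is right.

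The retention, completion, attrition and satisfaction points are secondary clarifications. At n=30 with no withdrawals, an on-study count can read 100% where a questionnaire count falls below 70%, but the response patterns are assumed and the plan adopts neither count.

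**What to change.** **Main change.** Reconcile Section 2 (Intervention), Section 4 (Participant App Usage) and the participant instructions to one daily figure. This costs an edit to one of the two sections and a check of the instructions and tip sheet.

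**Secondary clarifications**, to be written before rates are seen:

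- In Section 3 (Outcomes), define retention and completion as follow-up questionnaires obtained, divided by all consenting participants, naming the visit or visits for each. Say what counts as obtained, given that questions may be skipped.
- In Section 3 (General approach), say that attrition will be derived from the flags for tasks not completed.
- Name the Week 6 satisfaction item and say whether 70% is a share of participants or a score.
- State whether an AIM average of 4 or more is supportive of the satisfaction criterion in the Outcomes paragraph.

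This takes a few sentences and needs no new visits, data or participants. With questionnaire-based definitions, reported retention will be equal to or lower than an on-study count.
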